#### **Concomitant medications**

• By-subject listing of past and concomitant medication including subject ID, site, trade name, dose, units, frequency, route, start date and time, end date and time, whether ongoing, indication.

## 9.4 Efficacy

#### 9.4.1 Primary Efficacy Analysis

Primary efficacy analysis will be conducted on mITT population. Because this is an exploratory study, alpha will be set at 0.1 for comparisons between groups.

- For each of the treatment groups, the incidence of success/ failure will be calculated along with a 90% exact binomial confidence interval.
- Additionally, descriptive statistics of total Mayo Score Clinical Response (Stool Frequency, Rectal Bleeding, Endoscopic Finding, Physician's Global Assessment and total score) will be presented by visit and treatment group including two-sided 95% Exact Binomial confidence intervals.

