For numeric continuous endpoints: Descriptive statistics and summary tables will include sample size, arithmetic mean, standard deviation, median, minimum and maximum, and 95% Confidence Interval (CI) for mean at the relevant time points by treatment and placebo corrected for the active treatment group.

For ordered categories endpoints: incidences in the different categories and, after dichotomization into success/failure-like categories, incidence of failure and relative risk of failure in the active group towards placebo with 95% confidence intervals.

This is an exploratory trial whose main analyses will be descriptive in nature. Where statistical testing will be applied, an alpha of 0.1 will be considered significant. At the same time, this being an exploratory trial, there will be no correction for overall Type I Error. The data will be analyzed using the SAS® 9.1 (or higher) software package (SAS Institute, Cary, North Carolina).

Safety Endpoint Analysis

Safety endpoint analysis will be descriptive in nature and done on the safety anlysis set.

Effiacy Endpoints Analysis

Analysis of all efficacy endpoints will be performed on the mITT set. The PP set will be used as supplementary analyses to test the robustness of the results.

TABLE OF CONTENTS

			NATURE PAGE		
PR	OTO	COL VEI	RSION HISTORY	3	
PR	OTO	COL SYN	NOPSIS	7	
TA	BLE	OF CON	TENTS	13	
GL	OSSA	RY		16	
1.			TION		
1.			TIVE COLITIS		
	1.1	1.1.1	The Role of Eotaxin and Eosinophils in Inflammatory Bowel Disease		
	1.2		GATIONAL THERAPY		
		1.2.1	Nonclinical Studies		
		1.2.2	Clinical Studies		
	1.3	STUDY F	RATIONALE	19	
		1.3.1	Rationale for Dose Selection	19	
		1.3.2	Allergic and Infusion Reactions	20	
2.	STU	JDY OBJ	ECTIVES AND ENDPOINTS	20	
	2.1	STUDY (Objectives	20	
	2.2	STUDY E	ENDPOINTS AND OUTCOMES	20	
		2.2.1	Efficacy Endpoints		
		2.2.2	Pharmacokinetic Endpoints		
		2.2.3	Pharmacodynamic Endpoints		
		2.2.4	Safety Endpoints		
3.	STU	JDY DES	IGN	21	
4.	STU	JDY POP	ULATION	22	
	4.1	INCLUSION	on Criteria	22	
	4.2	EXCLUS	ION CRITERIA	22	
	4.3		IDENTIFICATION AND TREATMENT ALLOCATION		
	4.4	SCREEN	ING FAILURES	24	
	4.5	· · · · · · · · · · · · · · · · · · ·			
		ASSESSN	MENT		
		4.5.1	Handling of Early Discontinuation.		
		4.5.2	Adverse Events		
	4.6	SPONSOI	R'S TERMINATION OF STUDY	25	
5.	STU		OCEDURES AND ASSESSMENTS		
	5.1		ING PERIOD (VISIT 1, DAY -28 TO DAY -1)		
	5.2		ENT PERIOD: VISIT 2 (DAY 0), VISIT 3 (DAY 14) AND VISIT 4 (DAY 28)		

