8.3 STATISTICAL METHODS

All measured variables and derived parameters will be listed individually. Outcomes will be summarized by treatment group, depending on their nature, as follows:

- For dichotomous variables: Categorization into success/failure-like categories; then incidence of failure and relative risk of failure in the active group compared to placebo with 95% confidence interval.
- For numeric continuous endpoints: Descriptive statistics and summary tables will include sample size, arithmetic mean, standard deviation, median, minimum and maximum, and 95% Confidence Interval (CI) for mean at the relevant time points by treatment.
- For ordered categories endpoints: incidences in the different categories and, after dichotomization into success/failure-like categories, incidence of failure and relative risk of failure by treatment with 95% confidence intervals.

All tests applied will be two-tailed, and p value of 0.1 or less will be considered statistically significant. Since this is an exploratory trial, there will be no Alpha-correction for multiple testing. The data will be analyzed using the SAS® 9.1 software package or higher (SAS Institute, Cary, North Carolina).

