8.3.4.1 Primary Endpoint Analysis

This study's primary endpoint analyses will be descriptive, providing proportion of Mayo Score Clinical Response separately by treatment group, including two-sided 95% Exact

Protocol: Immune/BRT/UC-01 Page 40 of 58 Final Version 8.0 May 23, 2018

^o a) The continuous UCEIS will be imputed using MI, after which clinical response will be computed and b) Should there be variables causing the MI model not to converge, these will be excluded from the model.

Binomial confidence intervals. Exploratory statistical testing will be done by comparing Bertilimumab treatment arm to placebo.

8.3.4.2 Secondary Endpoint Analyses

- a. Primary endpoint analysis described in the preceding section will be repeated in PP.
- b. Secondary endpoints will be analysed in both mITT and PP analysis sets.

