#### 1 Introduction

#### 1.1 General

Ulcerative colitis (UC) is a chronic and relapsing inflammatory disease characterized by diffuse mucosal inflammation limited to the colon and rectum without evidence of any specific causative pathogens.

Bertilimumab is the first monoclonal antibody to specifically neutralize human eotaxin-1 to enter clinical trials. Bertilimumab has been shown to interrupt the eotaxin-stimulated migration of cells and may therefore be useful in the treatment of human diseases such as UC, where eosinophil accumulation is an important feature.

This is the first study investigating clinical outcome of treatment with bertilimumab in UC patients. The purpose of this study is to evaluate the safety and efficacy of bertilimumab compared to placebo in adult patients with active moderate to severe UC. In addition, the pharmacokinetics (PK) and pharmacodynamics (PD) of bertilimumab will be assessed throughout the study.

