## 9 Statistical Analysis

All descriptive statistics will be provided by treatment group and overall, as relevant.

Numerical variables will be tabulated using mean, standard deviation, minimum, median, maximum and number of observations. Categorical variables will be tabulated using number of observations and percentages.

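### The SAP sets alpha at 0.1 for comparing the arms but specifies no between-arm estimate, interval or test, and drops the protocol's relative risk and test against placebo.

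*SAP*

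**What the plan says.** **SAP.** Section 1.1 gives the purpose as to "evaluate the safety and efficacy of bertilimumab compared to placebo in adult patients with active moderate to severe UC". Section 9.4.1 states "Because this is an exploratory study, alpha will be set at 0.1 for comparisons between groups". The outputs that follow are one-arm summaries. The first is "For each of the treatment groups, the incidence of success/ failure will be calculated along with a 90% exact binomial confidence interval"; the second is a table of Mayo total and sub-scores by visit and arm. The general rule in section 9 is "All descriptive statistics will be provided by treatment group and overall, as relevant". Section 9.4.2 repeats the per-arm intervals at 95% and in the PP set, and adds frequencies and descriptive tables. Section 9.4.5 shows the primary endpoint by covariate level, again descriptively.

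**Protocol.** Section 8.3 plans, for dichotomous outcomes, "incidence of failure and relative risk of failure in the active group compared to placebo with 95% confidence interval". It adds "All tests applied will be two-tailed, and p value of 0.1 or less will be considered statistically significant". Section 8.3.4.1 makes the primary analysis descriptive by arm, with 95% exact intervals, and then says "Exploratory statistical testing will be done by comparing Bertilimumab treatment arm to placebo". It names no test. Section 8 leaves the full detail of the analyses to the SAP.

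**Change in total Mayo score.** SAP 7.3 defines it as a secondary endpoint. SAP 9.4.2 has output lines for change in UCEIS and change in partial Mayo, but none for this.

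**The concern.** The stated alpha is attached to no analysis. The trial randomizes against placebo in order to compare with placebo, and the SAP as written stops at two separate proportions. A reader of the resulting tables would have to compare the two intervals by eye, which is not a comparison at level 0.1, or calculate the contrast after seeing the data. The protocol fixes the effect measure, the 95% interval, two-sidedness and alpha. Neither document fixes the test, or whether it uses prior anti-TNF treatment, the randomization stratum. Those choices stay open until someone makes them, possibly after unblinding.

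**Working it through.** **Text check.** Contrasts in the protocol, set against the SAP:

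| Protocol | SAP |
|---|---|
| Relative risk of failure against placebo, 95% CI (8.3) | Absent |
| Exploratory test against placebo (8.3.4.1) | Absent; only the alpha survives (9.4.1) |
| Per-arm response with 95% exact CI (8.3.4.1) | Present, at 90% (9.4.1) and 95% (9.4.2) |

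**Inputs.** Up to 42 subjects (protocol 8.2) at 2:1 give 42 × 2/3 = 28 and 42 × 1/3 = 14. This assumes that all 42 are enrolled and in the mITT set. The current documents state no response rates, effect size or power, so there is no planned figure to reproduce and all rates below are assumptions.

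**Do two per-arm 90% intervals stand in for a comparison?** All 29 × 15 possible outcomes were enumerated with binomial probabilities. The non-overlap rule calls a difference when the two Clopper-Pearson 90% intervals do not overlap. Fisher and pooled chi-square call it at p of 0.1 or less.

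Type I error with the same true response rate in both arms:

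| Common rate | Non-overlap | Fisher | Chi-square |
|---|---|---|---|
| 20% | 0.5% | 6.8% | 10.1% |
| 30% | 0.9% | 7.3% | 10.3% |
| 40% | 1.1% | 7.0% | 10.2% |
| 50% | 1.1% | 5.9% | 10.2% |

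Power, active versus placebo:

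| Rates | Non-overlap | Fisher | Chi-square |
|---|---|---|---|
| 50% vs 30% | 9% | 26% | 35% |
| 60% vs 30% | 24% | 48% | 59% |
| 50% vs 20% | 25% | 53% | 62% |

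**Worked example, 16/28 versus 4/14 responders (57% versus 29%).**

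- What the SAP reports: 90% exact intervals of 40-73% and 10-54%. They overlap, and no contrast is given.
- Relative risk of failure: (12/28) / (10/14) = 0.60.
- Standard error of its log: √(1/12 − 1/28 + 1/10 − 1/14) = 0.276.
- 95% CI: 0.60 × exp(±1.96 × 0.276) = 0.35 to 1.03.
- 90% CI: 0.60 × exp(±1.645 × 0.276) = 0.38 to 0.94.
- Tests: Fisher p = 0.108, chi-square p = 0.081.

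In this example the call at 0.1 turns on a test that neither document names. The example was chosen near the boundary. With 14/28 versus 4/14, the relative risk is 0.70 (95% CI 0.43-1.15) and Fisher p is 0.32; chi-square, at 0.19, also stays above 0.1.

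**How much does the open choice of test matter?** At 28 versus 14, Fisher and chi-square disagree at 0.1 in 9%, 11% and 6% of trials at 50%, 60% and 70% versus 30%. Taking the smallest p among Fisher, mid-p and chi-square gives a type I error of 10.2-11.4% for null rates of 20-50%, against a nominal 10%.

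**Change in total Mayo.** SAP 9.4.1 already tabulates total Mayo by visit and arm. With the same subjects at both visits, mean change is the difference of two tabulated means. Mainly the SD of the change and the between-arm difference are missing.

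**The case against.** The strongest reply is that this is an exploratory, descriptive phase 2a trial and that the core of its primary analysis was carried over. Protocol 8.3.4.1 asks first for response by arm with 95% exact intervals, and the SAP supplies these. The reported counts let anyone compute the relative risk or an unstratified two-by-two test, no decision rule depends on p, and the protocol's own plan has not been withdrawn. All of this stands, and it limits the consequence. It does not remove the gap. The protocol's descriptive plan itself includes a relative risk with an interval, and a test left unnamed in the protocol can be fixed in advance only in the SAP.

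Four stronger readings are tempting, and the documents do not support them:

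- *That the unnamed test opens the way to serious selective reporting.* The inflation is at most about 1.4 points at 28 versus 14.
- *That placebo-corrected means were also dropped from the protocol's plan.* The phrase "at the relevant time points by treatment and placebo corrected for the active treatment group" stands only in the synopsis. Section 8.3 in the protocol body gives means by treatment. This is an inconsistency between synopsis and body.
- *That change in total Mayo is lost.* It is largely recoverable from the by-visit table and fully from the listings in SAP 10.
- *That prior anti-TNF treatment is ignored.* SAP 9.4.5 shows the primary endpoint by it. What is unstated is whether the comparison of arms uses it.

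**Conclusion.** The point holds as an unexplained omission between protocol and SAP. SAP 9.4.1 sets a level for a comparison that the SAP never specifies, so the SAP as written yields no estimate of effect against placebo. The per-arm intervals do not replace one: at 28 versus 14 their non-overlap has about 0.5-1.1% type I error, and 24% power at 60% versus 30%, where a direct test has 48-59%. These figures rest on assumed rates and full enrolment into the mITT set. The main loss is the missing effect estimate; the unnamed test is secondary. It is worth fixing because the fix is nearly free, but nothing here invalidates the trial or any conclusion it is designed to reach.

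**What to change.** Before unblinding, in SAP 9.4.1:

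1. Restore the relative risk of failure, active versus placebo, with the protocol's 95% interval, and state the interval method. A risk difference or an additional 90% interval is optional. The 90% interval would match alpha 0.1; if both levels are shown, say in advance how a disagreement is read, since in the worked example the 95% interval includes 1 and the 90% interval does not.
2. Name one fully defined two-sided test at 0.1, labelled exploratory, and state whether it is stratified by prior anti-TNF treatment.

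In SAP 9.4.2, as a minor addition, include change in total Mayo from screening to Day 56 by arm (mean and SD) with the between-arm difference. Separately, align the protocol synopsis and section 8.3 on the placebo-corrected summary.

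The cost is a few lines of SAP text and little programming; the data are already collected and the per-arm tables stay. The downside is that the contrast will be imprecise. In the worked example, a 29-point difference has a simple 90% interval of 29 ± 1.645 × 15.3, or about 25 points either side. A stratified version may be unstable if few subjects have had anti-TNF treatment.

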## 9.4.2 Secondary Efficacy Analysis

Secondary efficacy analysis will be conducted on mITT and PP populations.

- Primary analysis will be repeated using a 95% exact binomial confidence interval.
- Primary analysis will be repeated on PP population and with both 90% and 95% exact binomial confidence intervals.
- Frequency distribution of patient who had UCEIS assessments by visit and treatment group.
- Descriptive statistics of UCEIS score (Vascular pattern, Bleeding, Erosions & Ulcers and total score) by visit, treatment group.
- Descriptive statistics of change in UCEIS score (Vascular pattern, Bleeding, Erosions & Ulcers and total score) from screening to Day 56 (visit 7) by treatment group.
- Frequency distribution of dichotomous clinical remission at Day 56 (Visit 7) as defined in section 7.3.
- Frequency distribution of dichotomous mucosal healing at Day 56 (Visit 7) as defined in section 7.3.
- Descriptive statistics of partial Mayo score (Stool Frequency, Rectal Bleeding, Physician's Global Assessment and total of these sub-scores) by visit and treatment group.
- Descriptive statistics of change in partial Mayo score by visit and treatment group.

### 9.4.3 Pharmacokinetics (PK)

• Descriptive statistics of PK parameters as described in section 7.4 by visit, time point and treatment group.

## 9.4.4 Pharmacodynamics (PD)

• Descriptive statistics of PD parameters as described in section 7.5 by visit, time point and treatment group.

## 9.4.5 Covariate Analysis

The primary and secondary analysis will be conducted on the mITT population, and examine the following covariates:

Age

- Gender
- Prior TNF treatment
- Screening total Mayo score
- Screening UCEIS total score
- Screening tissue Eotaxin-1 levels
- Screening tissue Eosinophil count
- Baseline fecal calprotectin levels (visit 2)
- Baseline Hs-CRP (visit 2)
- Combined Site

For each of the listed above covariates descriptive statistics of primary endpoint/s by covariate levels will be presented. Continuous covariates will be divided into quartiles for this presentation.

# 10 Data Listings

Data listings will be provided for all data available from the CRF.

# 11 Computer Software

All statistical analyses will be carried out using SAS® Version 9.4 or higher under Windows® 2016 Terminal.
